### 2.3.2. Benefit Assessment

The proposed doses in this study are targeting steady-state exposures comparable to **CCI** mg **CCI** in adults, which were found to robustly decrease viral load and alleviate RSV symptoms relative to placebo (C5241002). On this basis, the potential benefit to individual study participants who receive active treatment may include a shorter time to clinical recovery, prevention of hospitalization, and a lower probability of progressing to more severe illness or death. The potential benefit of the study is that it may provide a new treatment option for pediatric participants with RSV-LRTI.

### 2.3.3. Overall Benefit/Risk Conclusion

Taking into account an unprecedented surge in pediatric RSV infections during 2022-2023, an unmet need for treatment of RSV infection, and the measures to minimize risk to study participants, the potential risks identified in association with sisunatovir in this dose-finding study are justified by the anticipated benefits in the clinical development of sisunatovir for the pediatric population with RSV-LRTI.

There are currently no approved RSV antivirals available, and thus no active control can be proposed as comparator. The comparator for this study is participants receiving placebo. Each cohort evaluated in the study will have participants on placebo. The placebo group is required for assessing the safety, tolerability, and palatability of the study intervention. All participants (including participants receiving placebo) enrolled in the study will receive the SOC.

## 3. OBJECTIVES, ENDPOINTS, AND ESTIMANDS

| Objectives   | Endpoints  | Estimands  |
|--|--|--|
| Primary:
To evaluate the safety and tolerability of sisunatovir compared to placebo in participants with RSV-LRTI. | Primary: 

Incidence of TEAEs.

Incidence of AEs and SAEs leading to discontinuations.

Incidence of clinically significant abnormal laboratory values and vital signs.

 | Primary: 

Not applicable

   |
| Secondary:
To characterize the PK of sisunatovir in participants with RSV-LRTI.                                    | Secondary: 

Plasma concentrations of sisunatovir at steady state (Day CCI or later).

  | Secondary: 

Not applicable

 |
| Tertiary:
To describe the viral load in NP samples over time in participants with RSV-LRTI.                        | Tertiary: 

Viral load measured via RT-qPCR in NP swabs over time (including but not limited to change from baseline at each sampled visit and proportion of

                          | Tertiary: 

Not applicable

  |

| Objectives   | Endpoints  | Estimands  |
|--|--|--|
|  | participants with BLOQ at Day [REDACTED]
[REDACTED]   |  |
| To describe signs and symptoms assessed by HCP over time in participants with RSV-LRTI       | 

Signs and symptoms over time (including but not limited to change from baseline at Day [REDACTED] and proportion of participants with each sign at Day [REDACTED])

 | 

Not Applicable

 |
| To assess the overall palatability of prepared oral dispersion in participants with RSV-LRTI | 

Responses to palatability questionnaire (eg, participant response to medication) at all time points (specified in protocol).

                                       | 

Not applicable

 |
| CCI [REDACTED]
[REDACTED]   | 

CCI [REDACTED]
[REDACTED]

Viral load in NP swabs and RSV signs and symptoms over time in participants CCI [REDACTED]
[REDACTED]

                    | 

Not applicable

 |

## 4. STUDY DESIGN

### 4.1. Overall Design

This study is a randomized, double-blind, sponsor-open, placebo-controlled, multicenter study in RSV-infected outpatient and hospitalized neonates, infants, and children, aged 1 day up to 60 months of age with RSV-LRTI; this is a dose finding study to evaluate the PK, safety, and tolerability of sisunatovir.

CCI [REDACTED]  
[REDACTED]

- Cohorts 1 and 2:

A: CCI [REDACTED]  
[REDACTED]

B: [REDACTED]

C: [REDACTED]

D: [REDACTED]

- Cohort 3:

E: CCI [REDACTED]  
[REDACTED]

F: [REDACTED]

G: [REDACTED]

H: [REDACTED]

Although neonates are defined by the WHO as 0-27 days old [10] CCI [REDACTED]

Sisunatovir or placebo will be administered CCI in a CCI ratio, for a period of CCI [REDACTED] for all cohorts. Each cohort will enroll CCI participants in each dose group ( CCI active: CCI placebo). In case of recruitment challenges for any cohort in the study, a minimum of CCI participants will be enrolled CCI active: CCI placebo).

Sisunatovir doses expected to produce systemic steady-state exposures comparable to the CCI mg CCI adult dose will be evaluated in dosing Cohort 1. Cohorts 1A, 1B, and 1C will initiate in parallel. CCI will receive sisunatovir or placebo, expected to produce systemic steady-state exposures comparable to the CCI mg CCI in adults. The CCI [REDACTED] may be enrolled only after E-DMC review of Cohort CCI data.

Based on analysis of PK and safety data from Cohort 1, the optional Cohort 2 (2A, 2B, 2C, 2D) may be used for further dose refinement to more closely match the CCI mg dose in CCI or to gather additional data on doses used in Cohort 1. The dose for Cohort CCI will be based on Cohort CCI. Only CCI will be enrolled CCI in CCI. Dose regimens for Cohort 2 will be provided via a digital system (eg, IWRS) upon incorporation of additional data from adults (C5241006) into the PopPK model and conducting simulations. Doses in Cohort 2 will not exceed exposures found to be well tolerated in adults in Study C5241006.

The optional Cohort 3 (3E, 3F, 3B, 3D) may be used if additional data (exposure, safety, tolerability data) for a given dose in one or more of the CCI [REDACTED] is needed. The CCI in Cohort 3 focus on those ages most susceptible CCI [REDACTED] (less than CCI). The specific dose and CCI in the optional Cohort 3 will be determined upon review of Cohorts 1 and/or 2 PK and safety data but will not exceed exposures found to be well tolerated in adults in Study C5241006. Sponsor will determine which age groups in Cohort 3 need additional exposure, safety or tolerability data for a given dose. Dose regimens for Cohort 3 will be provided via a digital system (eg, IWRS).

The Sponsor will make the final decision of doses for the cohorts, including recommendation to repeat a dose or opening enrollment of the subsequent cohort. An independent external data monitoring committee (E-DMC) will review the unblinded safety and concentration data after completion of Day CCI visit for each cohort (approximately CCI participants, CCI participants if there are recruitment challenges) to ensure the safety of participants. The E-DMC approval of Sponsor's recommendation will be independently assessed for each of the different age groups and will be based on the safety/tolerability and concentration data (ie, CCI [REDACTED] [REDACTED] [REDACTED]). In the event that there is a safety signal of concern, all randomizations must be halted by the Sponsor until the E-DMC has completed their review and has recommended that further randomization may continue. An earlier meeting of the E-DMC can be convened, as warranted, and based on the results of the E-DMC review, the E-DMC may recommend to the Sponsor that a dose of sisunatovir be terminated. If Sponsor recommends repeating the dose, an additional CCI participants receiving active drug and

PFIZER CONFIDENTIAL

**CCI** placebo may be enrolled in the same age group within the same cohort (limit once per cohort).

Participants may be replaced at Sponsor discretion for the following reasons: if the participant's parent(s)/legal guardian withdraws consent, if the participant misses any dose before providing the **CCI** sample on Day **CCI** or **CCI** if the participant misses any PK samples, if IMP is discontinued, or if the participant's RSV test results at screening are not confirmed by the central laboratory RSV test result, if participant was exposed to a prohibited concomitant medication or if Day 1 RSV RNA level by RT-qPCR is less than the lower limit of quantification.

Participant(s) with discrepant central laboratory RSV test result will not be included in the primary analysis.

For each participant, the study will have a maximum duration of approximately 5 weeks. This includes a screening period of 1-2 days, a **CCI** day Treatment period and a **CCI** follow-up period **CCI**. The highest, well-tolerated dose will be determined for the corresponding age band in this study.

Approximately a maximum of 108 participants **CCI** in each cohort + **CCI** additional in each cohort if necessary) will be enrolled. The minimum number of participants (based on a minimum of **CCI** participants per Cohort) is approximately **CCI** evaluable participants as Cohorts 2 (2A, 2B, 2C) and 3 (3E, 3F, 3B, 3D) are optional in the study.

The study will be conducted as a double-blind, sponsor-open study and will be conducted globally with the number of study sites yet to be determined. No study intervention will be provided to participants at the end of their study participation (Section 6.7).

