#### Safety Analysis:

All safety analyses will be performed on the safety analysis set, which is defined as all participants randomly assigned to study intervention and who take at least 1 dose of study

PFIZER CONFIDENTIAL

CT02-GSOP Clinical Protocol Template Phase 1 2 3 4 (14 April 2023)

Page 20

intervention. Participants will be analyzed according to the product (sisunatovir / placebo) they actually received.

AEs, blood pressure (BP), pulse rate, SpO2, and safety laboratory data will be reviewed and summarized on an ongoing basis during the study to evaluate the safety of participants. Any clinical laboratory or vital sign abnormality of potential clinical concern will be described. Safety data will be presented in tabular and/or graphical format and summarized descriptively, where appropriate.

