## 8.7. Biomarkers

Nasopharyngeal (NP) swabs for biomarker research are required and will be collected from all participants in this study as specified in the [SoA](#) in Section 1.3:

- **NP Swab Assessments**
  - A baseline NP swab sample (taken pre-dose) will be used to measure RSV RNA levels by quantitative RT-PCR, viral sequencing and to assess for RSV and other respiratory pathogens. This test will not be used to determine study eligibility. The pathogen panel assessment will be batched for analysis and the result will not be available to the sites for real time clinical management.
  - All NP swab samples will be analyzed to measure RSV RNA levels by quantitative RT-PCR (includes an internal quality control for sample collection) and will be utilized for viral sequencing to evaluate potential genetic viral variants. NP samples will be collected by an HCP during a site **CCI** /inpatient visit.
  - **CCI** [REDACTED]  
[REDACTED] and if permitted by local regulations. Human genetic analyses will not be performed on the NP samples.
  - Residuals of all NP samples may be retained beyond the end of the study to enable the analyses described above and related biomarker research on the study intervention and disease, if sufficient samples are available. Storage and shipping instructions will be in accordance with the laboratory manual. Genetic analyses will not be performed on these NP swab samples. Participant confidentiality will be maintained.

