## 9.2. Analysis Sets

For purposes of analysis, the following analysis sets are defined:

| Participant Analysis Set         | Description   |
|----------------------------------|---|
| Enrolled                         | "Enrolled" means a participant's, or their parent(s)/legal guardian's, agreement to participate in a clinical study following completion of the informed consent process and randomization.                         |
| Full analysis set                | All participants randomly assigned to study intervention and who take at least 1 dose of study intervention.  |
| Safety analysis set              | All participants randomly assigned to study intervention and who take at least 1 dose of study intervention. Participants will be analyzed according to the product (sisunatovir / placebo) they actually received. |
| PK Concentration Population      | All participants randomly assigned to study intervention and who take at least 1 dose of study intervention and in whom at least 1 concentration value can be reported.   |
| PK Parameter Analysis Population | All participants randomly assigned to study intervention and who take at least 1 dose of study intervention and in whom at least 1 of the PK parameters of interest can be reported.                                |
| Biomarker Analysis Population    | All participants randomly assigned to study intervention and who take at least 1 dose of study intervention and in whom at least 1 of the measured parameters of interest can be reported.                          |

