### **9.3.2. Primary Endpoint(s)**

The primary endpoints are related to safety/tolerability with analysis as described in Section 9.3.5

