### **9.3.5. Safety Analyses**

All safety analyses will be performed on the safety population.

AEs, BP, pulse rate, SPO2, and safety laboratory data will be reviewed and summarized on an ongoing basis during the study to evaluate the safety of participants. Any clinical laboratory and vital sign abnormalities of potential clinical concern will be described. Safety data will be presented in tabular and/or graphical format and summarized descriptively, where appropriate.

Medical history and physical examination and neurological examination information, as applicable, collected during the course of the study, will be considered source data and will not be required to be reported, unless otherwise noted. However, any untoward findings identified on physical and/or neurological examinations conducted during the active collection period will be captured as AEs, if those findings meet the definition of an AE. Data collected at screening that are used for inclusion/exclusion criteria, such as laboratory data, ECGs, and vital signs, will be considered source data, and will not be required to be reported, unless otherwise noted. Demographic data collected at screening will be reported. Data on premature birth and social factors collected at screening and during the study will be reported.

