6. ANALYSES AND SUMMARIES

6.1. Primary Endpoint(s)

All analyses of primary endpoints (safety analyses) will be performed on the safety population defined in Section 4.

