6.6. Baseline and Other Summaries and Analyses

6.6.1. Baseline Summaries

Demographic characteristics collected at screening will be summarized for the enrolled population in accordance with the sponsor reporting standards.

Data on premature birth and social factors collected at screening and during the study will be listed.

The number and percentages of participants infected with strain A, or B, or dual infected with A and B of RSV at baseline (pre-dose 1 swab) will be summarized. The number and percentages of participants with co-infections at baseline will also be summarized.

The number and percentage of participants who are inpatients (hospitalised) and outpatients at baseline, the duration of RSV symptoms at baseline, and whether on oxygen support at baseline will be summarized by cohort, treatment and age band.

The number and percentage of discrepancies between RSV diagnostic test results and Day 1 pre-dose NP swab results will be summarized by cohort, treatment and age band if applicable.

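### Protocol 4.1 removes children with a discrepant central RSV result from the primary analysis, but the primary endpoints are safety endpoints, analysed elsewhere on every dosed child

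*Protocol*

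**What the plan says.** Protocol 4.1 lists the reasons for which the sponsor may replace a participant and then adds: "Participant(s) with discrepant central laboratory RSV test result will not be included in the primary analysis."

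The analysis sections take a different line. Protocol 9.3.2 says "The primary endpoints are related to safety/tolerability with analysis as described in Section 9.3.5", and 9.3.5 says "All safety analyses will be performed on the safety population". Protocol 9.2 defines the safety analysis set as "All participants randomly assigned to study intervention and who take at least 1 dose of study intervention", grouped by the product actually received. The synopsis (Protocol 1.1) agrees: "All safety analyses will be performed on the safety analysis set, which is defined as all participants randomly assigned to study intervention", again with the one-dose condition.

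SAP 4 repeats the Protocol 9.2 definition, and SAP 6.1 says "All analyses of primary endpoints (safety analyses) will be performed on the safety population defined in Section 4". SAP 2.1 declares no departure from the protocol's analyses. The SAP takes up discrepant RSV results only in the baseline summaries of 6.6.1: "The number and percentage of discrepancies between RSV diagnostic test results and Day 1 pre-dose NP swab results will be summarized".

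**The concern.** The same dosed child is out of the primary analysis under one section and in it under the others.

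The plan foresees such children. Inclusion criterion 2 (Protocol 5.1) accepts a positive antigen or molecular test from routine site practice or a point-of-care kit. Of the pre-dose nasopharyngeal swab, Protocol 8.7 says "This test will not be used to determine study eligibility". A child can therefore be randomized and dosed before a disagreement with the central laboratory is known.

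In a descriptive study the incidence tables are the primary result, so the choice of denominator is the analysis. Removing a dosed child takes that child's adverse events out of the numerator and the exposure out of the denominator, although an unconfirmed RSV result does not undo the exposure. Protocol 6.4.3 and 9.4 also let the sponsor review unblinded data during the study, which is a further reason not to leave membership of the primary analysis open to choice.

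**Working it through.** This is a comparison of texts. No power or error-rate calculation applies, because there are no hypotheses (Protocol 9.1, SAP 5.1) and the sample size is empirical (Protocol 9.5).

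**1. What the primary analysis can mean.** Protocol 3 and SAP 2.2 and 3.1 list the primary endpoints: treatment-emergent adverse events, adverse events leading to discontinuation, and clinically significant laboratory and vital-sign abnormalities. All are safety endpoints. SAP 6.1 treats primary-endpoint analyses and safety analyses as the same thing. No other analysis in either document is labelled primary.

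**2. Who is in it.**

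| Place | Rule | RSV condition |
|---|---|---|
| Protocol 4.1 | Discrepant central result: left out of the primary analysis | Yes |
| Protocol 1.1, Safety Analysis | Randomized and at least one dose | None |
| Protocol 9.2 | Randomized and at least one dose | None |
| Protocol 9.3.5 | Safety population | None |
| SAP 4 | Randomized and at least one dose | None |
| SAP 6.1 | Safety population of SAP 4 | None |

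Protocol 9.3.5 says safety population where 9.2 says safety analysis set. SAP 6.1 ties the former term to SAP 4, whose definition matches 9.2, so the difference in naming does not explain the conflict.

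**3. Whether other text carries out or withdraws the exclusion.** The replacement paragraph appears three times (Protocol 1.1, 4.1, 9.5). The exclusion sentence appears in one of the three, 4.1. No analysis set in Protocol 9.2 or SAP 4 would implement it. The SAP version history cites an administrative change letter, PACL 11, dated 19 April 2024. That is 20 + 19 = 39 days after Amendment 4 (11 March 2024). The letter is not among the documents available and could have corrected the point; nothing that is available does.

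**4. Size.** The plan's only legible study-size figure is a maximum of about 108 evaluable participants. It cannot be rebuilt, because the cohort sizes are redacted. It can be spread over the 12 cohort and age-band cells in SAP 5.2: 108 / 12 = 9 children per cell on average, both arms together. One excluded child would be 1/9 = 11% of an average cell.

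The documents give no discrepancy rate. Purely as an assumption, take a share d of 2% to 20% and treat 108 as the number dosed:

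| Assumed d | Removed, 108 × d (rounded) | Left | Chance of at least one, 1 − (1 − d)^108 |
|---|---|---|---|
| 2% | 2 | 106 | 0.887 |
| 5% | 5 | 103 | 0.996 |
| 10% | 11 | 97 | above 0.99 |
| 20% | 22 | 86 | above 0.99 |

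This only shows that the two rules could give different denominators at modest rates. The 108 counts evaluable children, and with replacement the number dosed could be higher.

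**The case against.** The strongest reply is that Section 9 and the SAP are where the analysis is set, and they are clear. The chain from 9.3.2 to 9.3.5 to 9.2 is explicit, SAP 6.1 confirms it, and a programmer following the SAP has no choice to make. On this view the 4.1 sentence is a loose remark about evaluability, placed after replacement reasons that mostly concern PK sampling, dosing and virology, and no real table would change.

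Much of this stands. The SAP will probably be followed. The term is undefined, so the reading of 4.1 is an inference, although no text supports a different one. The statements that omit an RSV condition are not independent, since SAP 4 repeats Protocol 9.2. Protocol 8.7 does not itself call the baseline swab central; that link comes from the central laboratory wording in SAP 3.4.1 and the comparison in SAP 6.6.1.

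It does not remove the conflict. On the evaluability reading, the sentence still names an analysis that the plan does not contain. Protocol 9 allows the SAP to modify the protocol but expects major changes to primary-endpoint analyses to appear in an amendment as well, and SAP 2.1 says there are no changes. Measured against 4.1, that declaration is inaccurate.

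**Conclusion.** The point holds. Protocol 4.1 contains a current, legible exclusion rule that conflicts with Protocol 1.1, 9.2 and 9.3.5 and with SAP 4 and 6.1. The conclusion rests on reading the primary analysis as the analysis of the primary endpoints, the only reading the documents support, and on PACL 11 not having withdrawn the sentence.

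The consequence is confined to reporting. Adverse event collection and expedited reporting (Protocol 8.4.1), data monitoring committee review (4.1) and the stopping rules (4.1.1) carry no RSV condition, and no formal inference changes. How many children would be affected is unknown.

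**What to change.** Delete the sentence in Protocol 4.1, or state that it does not apply to the safety analysis set. If it was meant for another analysis, such as viral load, name that analysis and give it its own analysis set.

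Confirm in the same place that every dosed child, including one later replaced, stays in the safety analysis set whatever the central RSV result. Protocol 9.2 and SAP 4 and 6.1 already provide for this. If PACL 11 has made the correction, carry it into the next protocol version.

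The cost is one sentence in a clarification letter or the next amendment. It needs no new data and leaves the SAP safety tables as they are. The discrepancy counts in SAP 6.6.1 can stay as planned.

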#### 4.3. Justification for Dose

The current study will evaluate safety, tolerability, PK, and guidance for future dosing of sisunatovir in a broader pediatric population (1 day to 60 months of age) with RSV-LRTI for further clinical development of sisunatovir.

To investigate the effect of sisunatovir on clinical activity following RSV infection, a viral challenge clinical study in healthy adult participants was conducted where doses of 200 mg or 350 mg Q12 × 5 days were administered following inoculation of an RSV infection (C5241002). In this study, at both doses evaluated, sisunatovir robustly decreased viral load and alleviated RSV symptoms relative to placebo. While statistically significant differences were not observed between the two dose levels relative to placebo, the 350 mg dose effect was numerically larger than the 200 mg dose. Pediatric doses are expected to produce systemic steady-state exposures comparable to the adult dose of 200 mg q12h that was found to be effective in treating viral load and symptoms of RSV in the challenge study.

Additionally, sisunatovir was administered in a completed ex-US Phase 2 study (C5241003, previously REVC003) to characterize the PK profile, safety and virologic response to sisunatovir in RSV-infected hospitalized children aged 1 month -36 months. Participants 1 month to <6 months of age were administered sisunatovir up to 2.5 mg/kg q12h for 5 days. Participants 6 months to 36 months of age were administered sisunatovir up to 5.0 mg/kg q12h for 5 days. The highest dose in each age group provided mean exposures above EC90 and below the pre-specified upper exposure limit of 294 ng/mL. Overall, sisunatovir was found to be safe for infants and children ≥1 month to ≤36 months. These results support the current study to establish safety, tolerability, PK, and guidance for dosing of sisunatovir in a broader pediatric population (1 day up to 60 months) with RSV-LRTI for further clinical development of sisunatovir.

Initial pediatric dose recommendations for Cohort 1A, 1B, and 1C are based on observed concentrations in Study C5241003 with interpolation of predicted exposures, relative to

exposure of **CCI** mg **CCI** in adults. The proposed starting dose of sisunatovir for participants **CCI** is **CCI** mg/kg and for participants **CCI** is **CCI** mg/kg (see Table 4). These doses are **CCI** than those administered in **CCI**, which were well below the PK stopping limit NOAELs.

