### 9.5. Sample Size Determination

The sample size has been chosen empirically to provide safety and tolerability information and is not based on statistical power calculation. There will be up to three dosing cohorts (cohorts 2 [2A, 2B, 2C, 2D] and 3 [3E, 3F, 3B, 3D] are optional):

- Cohorts 1 and 2:

A: CCI

B:

C:

D:

[figure not shown]

- Cohort 3:

E: CCI

F:

B: **CCI**

D:

**CCI** participants (**cc** active, **cc** placebo) are planned for each cohort so that approximately **CCI** evaluable participants (**CC** per cohort) may be randomized into the study. The number randomized may be increased if Sponsor recommends repeating the dose for a cohort (ie, an additional **cc** active and **cc** placebo may be enrolled in the same cohort). This totals to approximately a maximum of 108 evaluable participants (**cc** in each cohort + **cc** additional in each cohort if necessary). The sample size for cohorts may be reduced to **CCI** active, **cc** placebo) if there are enrollment challenges. The minimum number of participants is approximately **CCI** evaluable participants (based on **cc** participants per Cohort) as Cohorts 2 (2A, 2B, 2C, 2D) and 3 (3E, 3F, 3B, 3D) are optional in the study.

Participants may be replaced at Sponsor discretion for the following reasons: if the participant's parent(s)/legal guardian withdraws consent, if the participant misses any dose before providing the **CCI** sample on Day **cc** or **cc** if the participant misses any PK samples, if the IMP is discontinued, if the participant's RSV test results at screening are not confirmed by the central laboratory RSV test result, if participant was exposed to a prohibited concomitant medication or if Day 1 RSV RNA levels by RT-qPCR is less than the lower limit of quantification.

Participants who discontinue from the study for non-safety reasons may be replaced at the sponsor's discretion in collaboration with the Investigator.

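### The protocol says the highest well-tolerated dose will be determined for each age band, but its exposure-matched, exposure-capped dose plan has no rule, endpoint or analysis that would identify one

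*Protocol*

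**What the plan says.** Protocol Section 4.1 makes an unqualified statement about what the trial will deliver: "The highest, well-tolerated dose will be determined for the corresponding age band in this study".

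The dose plan in Sections 4.1 and 4.3 is built on exposure:

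- **Cohort 1 (mandatory, bands A to D):** "Sisunatovir doses expected to produce systemic steady-state exposures comparable to the" adult reference dose. The figure is blacked out there, but Section 4.3 says: "Pediatric doses are expected to produce systemic steady-state exposures comparable to the adult dose of 200 mg q12h".
- **Cohort 2 (optional, A to D):** it "may be used for further dose refinement to more closely match the" adult reference, or to add data on doses already used in Cohort 1.
- **Cohort 3 (optional; 3E, 3F, 3B, 3D):** more exposure, safety or tolerability data for a given dose, with that dose set after review of Cohorts 1 and/or 2.

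Doses in Cohorts 2 and 3 are capped at exposures that adults tolerated well in Study C5241006. Section 6.6 rules out changing the dose within a cohort.

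On numbers, Section 9.5 says: "The sample size has been chosen empirically to provide safety and tolerability information and is not based on statistical power calculation". It also says, counting possible repeats: "This totals to approximately a maximum of 108 evaluable participants".

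**The concern.** To determine a highest well-tolerated dose, a design needs a definition of well tolerated, a set of dose levels that could reach or bracket the limit of tolerability, and a rule that selects one of them. Here the dose is driven by an exposure target and bounded by an adult-exposure cap. A band could tolerate every dose it receives, and the highest dose it could tolerate would still be unknown. If only Cohort 1 is run, the phrase can mean no more than the one dose given, provided that dose raised no problem.

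The stake is how the result is described. The study is meant to guide dosing in later pediatric trials. If this sentence carries through to the report, those trials could take a tolerability ceiling as established when the data show only how one or two exposure-matched doses behaved in a small group.

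**Working it through.** **Step 1. Look for the parts that the claim needs.**

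| Needed | What the documents contain |
|---|---|
| Objective or endpoint | None. Protocol Section 3 and SAP Section 2.2 list safety against placebo, plasma concentrations, and descriptive tertiary items. |
| Dose levels that step up | Section 4.1.1 allows for moving to a higher level, but no ladder is given. Cohort 2 refinement could go up or down. |
| Definition of well tolerated | None. Section 4.1.1 gives criteria for interrupting dosing or enrollment, two of them phrased in terms of dose-limiting intolerance. |
| Selection rule per band | None. The one criterion stated within an age band is a PK limit that blocks repeating or raising a dose. The clinical criteria are not tied to a band or dose level. |
| Analysis | None. SAP Section 5.1 has no hypotheses or decision rules, and SAP Sections 6.1.1 to 6.1.3 describe safety data. SAP Section 5.2 labels treatment only as placebo or sisunatovir, so dose shows only through cohort. |

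**Step 2. Reproduce the plan's figure.** The planned and additional numbers per cell are blacked out, so 108 cannot be rebuilt forward. Working backwards, there are 4 + 4 + 4 = 12 cohort-by-band cells, and 108/12 = 9 per cell. This assumes equal cells and counts placebo and one repeat.

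**Step 3. Convert to age bands.**

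- A and C (Cohorts 1 and 2): 2 × 9 = 18 each
- B and D (Cohorts 1, 2 and 3): 3 × 9 = 27 each
- E and F (Cohort 3 only): 9 each
- Check: 18 + 27 + 18 + 27 + 9 + 9 = 108
- Cohort 1 alone: at most 9 in each of A to D, or 36 in all

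The band lists in protocol Section 4.1 and SAP Section 2.3 label the last two Cohort 3 bands G and H. Elsewhere they are B and D. If G and H were separate bands, the ceiling for B and D would be 18.

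**Step 4. Precision at a dose actually tested (context only).** The active share is redacted. Assume 4 to 8 of 9 children are on active drug. The one-sided 95% upper limit after zero events is 1 − 0.05^(1/n). The chance of seeing no event at a true rate of 20% is 0.8^n. The chance of at least two affected children is 1 − 0.8^n − n × 0.2 × 0.8^(n−1).

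| Active n | Upper limit after 0 events | No event at true 20% | At least 2 affected at true 20% |
|---|---|---|---|
| 4 | 1 − 0.05^(1/4) = 53% | 0.8^4 = 41% | 18% |
| 6 | 1 − 0.05^(1/6) = 39% | 0.8^6 = 26% | 34% |
| 8 | 1 − 0.05^(1/8) = 31% | 0.8^8 = 17% | 50% |

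Two is the count used in four of the five interruption criteria in Section 4.1.1. These figures show that tolerability is only loosely characterised even at the dose given. They are not what defeats the claim: more children at the same dose would narrow the limits without showing whether a higher dose is tolerated.

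**The case against.** The strongest defence is that the documents contain more dose-finding machinery than a quick reading suggests. Section 4.1.1 contemplates a higher dose level, sets PK limits on progression, and lists countable criteria for intolerance. The E-DMC may recommend that a dose be terminated. Table 1 leaves the Cohort 2 dose to the sponsor and gives 2D the objective of assessing safety, PK and tolerability. Several target doses are blacked out, so a cell planned at a higher level cannot be excluded. Small descriptive cells are normal in Phase 1b, and the protocol is open about having no power calculation.

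Much of this stands, and it limits the point. A reader might infer that each band gets one dose in at most nine children. That is true only if the optional cohorts stay closed; nine is a ceiling per cell, not per band, and Cohort 2 may use a different dose. A reader might also infer that no escalation is possible, that no intolerance criteria exist, or that Cohort 3 simply repeats earlier doses. The documents support none of these. Nor is the small sample a defect in itself.

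None of it rescues the sentence. The criteria interrupt dosing or enrollment, and the E-DMC can rule a dose out. No provision turns these into a highest well-tolerated dose for a band. A sponsor could reply that the phrase means the highest tested dose that was tolerated, but the protocol does not say so.

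**Conclusion.** The claim in Section 4.1 is a property that the design does not have. This rests on the text: exposure-matched doses, a cap at adult exposures in Cohorts 2 and 3, and no ladder, selection rule, objective, endpoint or analysis. The figure of about nine children per cell is an inference from 108/12. The totals of 18 or 27 per band assume equal cells, every optional cohort and every repeat. The precision range of 31% to 53% rests on the assumed 4 to 8 active children.

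The consequence is moderate. The primary endpoints and their descriptive analysis are unaffected. A reader might infer that the report will state a highest well-tolerated dose. Nothing in the SAP carries the claim there, so this is a risk of overstatement and not a planned result.

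**What to change.** Reconcile the sentence in Section 4.1, and the reference to a higher dose level in Section 4.1.1, with the objectives in Section 3 and the dose plan in Sections 4.1 and 4.3. The stated conclusion should be limited to what the design supports, by age band: the safety and tolerability of the dose(s) tested, and how their steady-state exposure compares with the adult reference. If the sponsor wishes to keep the claim, the protocol must define the term and the decision rule behind it, and the SAP must say how it will be reported. No dose or clinical rule is proposed here.

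The cost is a small text change in two sections and a more modest claim. Limiting the conclusion in this way needs no change to cohorts, sample size or data collection.
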